7.20 **CLINICAL FOLLOW-UP DATA: Will clinical follow-up data be linked to specimens (i.e., will medical record information continue to be abstracted after the specimen is collected): (REQUIRED) © Yes © No Provide duration of follow-up or 'indefinitely': Indefinitely, as patients may return for use of their embryos for next child. 7.25 **STATISTICAL METHODS: Briefly summarize the methods and types of analyses that will be performed: This study will be a pilot study which will potentially lead to a larger randomized controlled trial. We expect N=20 to each group (cases and controls, respectively) and given low-stimulation protocols, expect 1-3 embryos per patient. Given these low numbers, summary statistics will be used. For categorical outcomes, frequency tables will be provided. For continuous outcomes, full summary statistics will be provided. This will include mean, standard deviation, minimum, maximum, median and quartiles. To determine the effect of IVC with INVOcell device versus conventional IVF while using oral stimulation or minimal gonadotropins stimulation protocols on: a. Fertilization rate, which is defined by the total number of fertilized oocytes divided by total number of mature oocytes retrieved. This comparison will take place on day-3, as that is when the IVC embryos will be assessed. b. Embryo quality. This is measured by the Gardner grading system. c. Implantation rate, which is defined by the number of fetal poles with heartbeat seen on ultrasound divided by tumber of embryos transferred d. Clinical pregnancy rate, which is defined by the number of fetal poles with heartbeat seen on ultrasound divided by the number of embryos transferred e. Live birth rate, which is defined by the number of living babies delivered divided by the number of transfers To determine the effect of IVC with INVOcell device versus conventional IVF while using oral stimulation or minimal gonadotropins stimulation protocols on: a. Live birth rate, which is defined by the number of living babies delivere		ter the study is
record information continue to be abstracted after the specimen is collected): (REQUIRED) ② Yes ③ No Provide duration of follow-up or 'indefinitely': Indefinitely, as patients may return for use of their embryos for next child. 7.25 STATISTICAL METHODS: Briefly summarize the methods and types of analyses that will be performed: This study will be a pilot study which will potentially lead to a larger randomized controlled trial. We expect N=20 to each group (cases and controls, respectively) and given low-stimulation protocols, expect 1-3 embryos per patient. Given these low numbers, summary statistics will be used. For categorical outcomes, frequency tables will be provided. For continuous outcomes, full summary statistics will be provided. This will include mean, standard deviation, minimum, maximum, median and quartiles. To determine the effect of IVC with INVOcell device versus conventional IVF while using oral stimulation or minimal gonadotropins stimulation protocols on: a. Fertilization rate, which is defined by the total number of fertilized oocytes divided by total number of mature oocytes retrieved. This comparison will take place on day-3, as that is when the IVC embryos will be assessed. b. Embryo quality. This is measured by the Gardner grading system. c. Implantation rate, which is defined by number gestational sacs seen on early pregnancy 6-week ultrasound divided by the number of embryos transferred d. Clinical pregnancy rate, which is defined by the number of fetal poles with heartbeat seen on ultrasound divided by the number of embryos transferred e. Live birth rate, which is defined by the number of living babies delivered divided by the number of transfers To determine the effect of IVC with INVOcell device versus conventional IVF while using oral stimulation or minimal gonadotropins stimulation protocols on: a. Live birth rate, which is defined by the number of live births divided by the number of transfers	O Yes • No	
Provide duration of follow-up or 'indefinitely': Indefinitely, as patients may return for use of their embryos for next child. 7.25 STATISTICAL METHODS: Briefly summarize the methods and types of analyses that will be performed: This study will be a pilot study which will potentially lead to a larger randomized controlled trial. We expect N=20 to each group (cases and controls, respectively) and given low-stimulation protocols, expect 1-3 embryos per patient. Given these low numbers, summary statistics will be used. For categorical outcomes, frequency tables will be provided. For continuous outcomes, full summary statistics will be provided. This will include mean, standard deviation, minimum, maximum, median and quartiles. To determine the effect of IVC with INVOcell device versus conventional IVF while using oral stimulation or minimal gonadotropins stimulation protocols on: a. Fertilization rate, which is defined by the total number of fertilized oocytes divided by total number of mature oocytes retrieved. This comparison will take place on day-3, as that is when the IVC embryos will be assessed. b. Embryo quality. This is measured by the Gardner grading system. c. Implantation rate, which is defined by unmber gestational sacs seen on early pregnancy 6-week ultrasound divided by number of embryos transferred d. Clinical pregnancy rate, which is defined by the number of fetal poles with heartbeat seen on ultrasound divided by the number of embryos transferred e. Live birth rate, which is defined by the number of fliving babies delivered divided by the number of transfers To determine the effect of IVC with INVOcell device versus conventional IVF while using oral stimulation or minimal gonadotropins stimulation protocols on: a. Live birth rate, which is defined by the number of live births divided by the number of transfers		
7.25 STATISTICAL METHODS: Briefly summarize the methods and types of analyses that will be performed: This study will be a pilot study which will potentially lead to a larger randomized controlled trial. We expect N=20 to each group (cases and controls, respectively) and given low-stimulation protocols, expect 1-3 embryos per patient. Given these low numbers, summary statistics will be used. For categorical outcomes, frequency tables will be provided. For continuous outcomes, full summary statistics will be provided. This will include mean, standard deviation, minimum, maximum, median and quartiles. To determine the effect of IVC with INVOcell device versus conventional IVF while using oral stimulation or minimal gonadotropins stimulation protocols on: a. Fertilization rate, which is defined by the total number of fertilized oocytes divided by total number of mature oocytes retrieved. This comparison will take place on day-3, as that is when the IVC embryos will be assessed. b. Embryo quality. This is measured by the Gardner grading system. c. Implantation rate, which is defined by number gestational sacs seen on early pregnancy 6-week ultrasound divided by number of embryos transferred d. Clinical pregnancy rate, which is defined by the number of fetal poles with heartbeat seen on ultrasound divided by the number of embryos transferred e. Live birth rate, which is defined by the number of living babies delivered divided by the number of transfers To determine the effect of IVC with INVOcell device versus conventional IVF while using oral stimulation or minimal gonadotropins stimulation protocols on: a. Live birth rate, which is defined by the number of live births divided by the number of transfers	⊙ Yes C No	
 7.25 STATISTICAL METHODS: Briefly summarize the methods and types of analyses that will be performed: This study will be a pilot study which will potentially lead to a larger randomized controlled trial. We expect N=20 to each group (cases and controls, respectively) and given low-stimulation protocols, expect 1-3 embryos per patient. Given these low numbers, summary statistics will be used. For categorical outcomes, frequency tables will be provided. For continuous outcomes, full summary statistics will be provided. This will include mean, standard deviation, minimum, maximum, median and quartiles. To determine the effect of IVC with INVOcell device versus conventional IVF while using oral stimulation or minimal gonadotropins stimulation protocols on: a. Fertilization rate, which is defined by the total number of fertilized oocytes divided by total number of mature oocytes retrieved. This comparison will take place on day-3, as that is when the IVC embryos will be assessed. b. Embryo quality. This is measured by the Gardner grading system. c. Implantation rate, which is defined by number gestational sacs seen on early pregnancy 6-week ultrasound divided by number of embryos transferred d. Clinical pregnancy rate, which is defined by the number of fetal poles with heartbeat seen on ultrasound divided by the number of embryos transferred e. Live birth rate, which is defined by the number of living babies delivered divided by the number of transfers To determine the effect of IVC with INVOcell device versus conventional IVF while using oral stimulation or minimal gonadotropins stimulation protocols on: a. Live birth rate, which is defined by the number of live births divided by the number of transfers 7.26 REFERENCES: List only the 5-10 most relevant references (a separate bibliography can be attached for reference purposes if this study involves novel approaches, agents, or an emerg	Provide duration of follow-up or 'indefinitely':	
This study will be a pilot study which will potentially lead to a larger randomized controlled trial. We expect N=20 to each group (cases and controls, respectively) and given low-stimulation protocols, expect 1-3 embryos per patient. Given these low numbers, summary statistics will be used. For categorical outcomes, frequency tables will be provided. For continuous outcomes, full summary statistics will be provided. This will include mean, standard deviation, minimum, maximum, median and quartiles. To determine the effect of IVC with INVOcell device versus conventional IVF while using oral stimulation or minimal gonadotropins stimulation protocols on: a. Fertilization rate, which is defined by the total number of fertilized oocytes divided by total number of mature oocytes retrieved. This comparison will take place on day-3, as that is when the IVC embryos will be assessed. b. Embryo quality. This is measured by the Gardner grading system. c. Implantation rate, which is defined by number gestational sacs seen on early pregnancy 6-week ultrasound divided by number of embryos transferred. d. Clinical pregnancy rate, which is defined by the number of fetal poles with heartbeat seen on ultrasound divided by the number of embryos transferred. e. Live birth rate, which is defined by the number of living babies delivered divided by the number of transfers To determine the effect of IVC with INVOcell device versus conventional IVF while using oral stimulation or minimal gonadotropins stimulation protocols on: a. Live birth rate, which is defined by the number of live births divided by the number of transfers	Indefinitely, as patients may return for use of their embryos for next child.	
We expect N=20 to each group (cases and controls, respectively) and given low-stimulation protocols, expect 1-3 embryos per patient. Given these low numbers, summary statistics will be used. For categorical outcomes, frequency tables will be provided. For continuous outcomes, full summary statistics will be provided. This will include mean, standard deviation, minimum, maximum, median and quartiles. To determine the effect of IVC with INVOcell device versus conventional IVF while using oral stimulation or minimal gonadotropins stimulation protocols on: a. Fertilization rate, which is defined by the total number of fertilized oocytes divided by total number of mature oocytes retrieved. This comparison will take place on day-3, as that is when the IVC embryos will be assessed. b. Embryo quality. This is measured by the Gardner grading system. c. Implantation rate, which is defined by number gestational sacs seen on early pregnancy 6-week ultrasound divided by number of embryos transferred. d. Clinical pregnancy rate, which is defined by the number of fetal poles with heartbeat seen on ultrasound divided by the number of embryos transferred. e. Live birth rate, which is defined by the number of living babies delivered divided by the number of transfers. To determine the effect of IVC with INVOcell device versus conventional IVF while using oral stimulation or minimal gonadotropins stimulation protocols on: a. Live birth rate, which is defined by the number of live births divided by the number of transfers		ill be
summary statistics will be provided. This will include mean, standard deviation, minimum, maximum, median and quartiles. To determine the effect of IVC with INVOcell device versus conventional IVF while using oral stimulation or minimal gonadotropins stimulation protocols on: a. Fertilization rate, which is defined by the total number of fertilized oocytes divided by total number of mature oocytes retrieved. This comparison will take place on day-3, as that is when the IVC embryos will be assessed. b. Embryo quality. This is measured by the Gardner grading system. c. Implantation rate, which is defined by number gestational sacs seen on early pregnancy 6-week ultrasound divided by number of embryos transferred d. Clinical pregnancy rate, which is defined by the number of fetal poles with heartbeat seen on ultrasound divided by the number of embryos transferred e. Live birth rate, which is defined by the number of living babies delivered divided by the number of transfers To determine the effect of IVC with INVOcell device versus conventional IVF while using oral stimulation or minimal gonadotropins stimulation protocols on: a. Live birth rate, which is defined by the number of live births divided by the number of transfers	We expect N=20 to each group (cases and controls, respectively) and given low-stimulation protocols, expect 1-3 embryos per patient. Given these low numbers, summary statistics will be	
a. Fertilization rate, which is defined by the total number of fertilized oocytes divided by total number of mature oocytes retrieved. This comparison will take place on day-3, as that is when the IVC embryos will be assessed. b. Embryo quality. This is measured by the Gardner grading system. c. Implantation rate, which is defined by number gestational sacs seen on early pregnancy 6-week ultrasound divided by number of embryos transferred d. Clinical pregnancy rate, which is defined by the number of fetal poles with heartbeat seen on ultrasound divided by the number of embryos transferred e. Live birth rate, which is defined by the number of living babies delivered divided by the number of transfers To determine the effect of IVC with INVOcell device versus conventional IVF while using oral stimulation or minimal gonadotropins stimulation protocols on: a. Live birth rate, which is defined by the number of live births divided by the number of transfers	summary statistics will be provided. This will include mean, standard deviation, minimum,	
number of mature oocytes retrieved. This comparison will take place on day-3, as that is when the IVC embryos will be assessed. b. Embryo quality. This is measured by the Gardner grading system. c. Implantation rate, which is defined by number gestational sacs seen on early pregnancy 6-week ultrasound divided by number of embryos transferred d. Clinical pregnancy rate, which is defined by the number of fetal poles with heartbeat seen on ultrasound divided by the number of embryos transferred e. Live birth rate, which is defined by the number of living babies delivered divided by the number of transfers To determine the effect of IVC with INVOcell device versus conventional IVF while using oral stimulation or minimal gonadotropins stimulation protocols on: a. Live birth rate, which is defined by the number of live births divided by the number of transfers 7.26 REFERENCES: List only the 5-10 most relevant references (a separate bibliography can be attached for reference purposes if this study involves novel approaches, agents, or an emerging technology		
 c. Implantation rate, which is defined by number gestational sacs seen on early pregnancy 6-week ultrasound divided by number of embryos transferred d. Clinical pregnancy rate, which is defined by the number of fetal poles with heartbeat seen on ultrasound divided by the number of embryos transferred e. Live birth rate, which is defined by the number of living babies delivered divided by the number of transfers To determine the effect of IVC with INVOcell device versus conventional IVF while using oral stimulation or minimal gonadotropins stimulation protocols on: a. Live birth rate, which is defined by the number of live births divided by the number of transfers 7.26 REFERENCES: List only the 5-10 most relevant references (a separate bibliography can be attached for reference purposes if this study involves novel approaches, agents, or an emerging technology 	number of mature oocytes retrieved. This comparison will take place on day-3, as that is	
 d. Clinical pregnancy rate, which is defined by the number of fetal poles with heartbeat seen on ultrasound divided by the number of embryos transferred e. Live birth rate, which is defined by the number of living babies delivered divided by the number of transfers To determine the effect of IVC with INVOcell device versus conventional IVF while using oral stimulation or minimal gonadotropins stimulation protocols on: a. Live birth rate, which is defined by the number of live births divided by the number of transfers 7.26 REFERENCES: List only the 5-10 most relevant references (a separate bibliography can be attached for reference purposes if this study involves novel approaches, agents, or an emerging technology 	c. Implantation rate, which is defined by number gestational sacs seen on early pregnancy 6-	
 a. Live birth rate, which is defined by the number of live births divided by the number of transfers 7.26 REFERENCES: List only the 5-10 most relevant references (a separate bibliography can be attached for reference purposes if this study involves novel approaches, agents, or an emerging technology 	d. Clinical pregnancy rate, which is defined by the number of fetal poles with heartbeat seen on ultrasound divided by the number of embryos transferrede. Live birth rate, which is defined by the number of living babies delivered divided by the	
 7.26 REFERENCES: List only the 5-10 most relevant references (a separate bibliography can be attached for reference purposes if this study involves novel approaches, agents, or an emerging technology 		
for reference purposes if this study involves novel approaches, agents, or an emerging technology		
	for reference purposes if this study involves novel approaches, agents, or an emergin	

- 1. Mascarehas, M.N., et al., *National, Regional, and Global Trends in Infertility Prevalence Since 1990: A Systematic Analysis of 277 Health Surveys.* PLOS Medicine, 2012. 9(12): p. e1001356.
- 2. Unisa, S., *Childlessness in Andhra Pradesh, India: Treatment-seeking and consequences.* Reproductive Health Matters, 1999. 7(13): p. 11.
- 3. Asemota, O.A. and P. Klatsky, *Access to infertility care in the developing world: the family promotion gap.* Seminars in Reproductive Medicine, 2015. 33(1): p. 6.

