7.1	This new consolidated section requests information about: • Hypothesis • Aims • Study Design • Background and Significance • Preliminary Studies • Procedures • Statistical Methods • References Later sections include: • Drugs and Devices • Sample Size, Eligibility, and Subjects • Recruitment and Consent • Risks and Benefits • Data and Safety Monitoring Plan • Confidentiality, Privacy and Security • Financial Considerations • Qualifications of Personnel • Other Approval and Registrations	
7.2	HYPOTHESIS: Describe the hypothesis or what the study hopes to prove (Help Text updated 9/13)	:
In v	women with infertility requiring IVF or same-sex couples requiring IVF, we will see similar	

ı

7.3 AIMS: List the specific aims:

PRIMARY AIM:

To determine the outcomes of IVC with INVOcell device versus conventional IVF while using oral stimulation or minimal gonadotropins stimulation protocols on:

a. Implantation rate

SECONDARY AIMS:

To determine the outcome of IVC with INVOcell device versus conventional IVF while using oral stimulation or minimal gonadotropins stimulation protocols on:

- a. Fertilization rate
- b. Embryo quality
- c. Clinical pregnancy rate
- d. Live birth rate
- 7.4 DESIGN: Briefly describe the study design (e.g., observational, interventional, randomized, placebocontrolled, blinded, cross-over, cross-sectional, longitudinal, pharmacokinetic, etc.):

Non-blinded prospective randomized controlled trial pilot study

7.5 BACKGROUND AND SIGNIFICANCE: Briefly provide the background and significance of this study (e.g. why is this study needed) (space limit: one half page):

If this is a first in humans study, please summarize the safety data from the animal studies. For pediatric drug or device studies, please identify if this is the first study in pediatric populations.

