IVC, also called INVO, was developed by Claude Ranoux in 1988 as another method for culturing oocytes or embryos when compared to the conventional laboratory culture method [5]. Since then, the device has been used and studied in multiple countries including: Austria, Bolivia, Brazil, Canada, Ecuador, India, Mexico, Nicaragua, Pakistan, Panama, Spain, Turkey, and Venezuela [5-8]. In addition, INVOcell was FDA approved for use in the United States in November of 2015. There have been numerous studies on the INVO procedure and INVOcell device including evaluation and optimal conditions of the culture such as pH, pCO2 and pO2 [8] to optimal time of intra-vaginal culture [9]. Garcia-Ferreyra et al performed a prospective, non-randomized study that evaluated INVO using intracytoplasmic sperm injection (ICSI) with INVOcell versus conventional ICSI to day 3 and found no significant differences between embryo quality (77% INVO-ICSI versus 86.8% ICSI), pregnancy rate (54.2% INVO-ICSI versus 58.1% ICSI) and implantation rate (31.7% INVO-ICSI versus 33.6% ICSI) [10]. To control for factors between patients, a pilot study performed in 2015, compared sister ocytes (INVO vs IVF) and found similar cleavage rates (93% ± 1.5% IVF versus 97% ± 6% INVO) and a clinical pregnancy rate of 43% per embryo transferred from INVO procedure. In the United States, the device has been FDA approved for IVC for three days, but there is currently research being done to investigate whether IVC for five days (to blastocyst stage) can lead to improved embryo quality and live birth rates. Doody et al performed a randomized controlled trial comparing IVF to IVC that showed no significant differences in the percentage quality of blastocyst transferred when compared to IVF (87.9% IVC, 97.2%, p = 0.09) and live birth rate (55 % IVC, 60 % IVF) [9]. In fact, the implantation and birth rates per blastocyst transferred was actually higher with INVOcell wersus IVF (54.5 versus 44.4% and 48.5 versus 41.7%) [9]. These findings are promising and show that	
7.7 * TREATMENT PROTOCOL: Is this a treatment study, i.e. does this study intend to provid to individuals with a medical or psychological condition: (REQUIRED)	e treatment
⊙ Yes ○ No	
7.8 * COMMON RESEARCH ACTIVITIES: Types of research activities that will be carried out. apply and describe in more detail in the 'Procedures / Methods' section: (REQUIRED)	Check all that

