 □ Interviews, questionnaires, surveys □ Educational or cognitive tests □ Focus groups ☑ Observation ☑ Non-invasive imaging or testing (MRI, EEG, pulse oximetry, etc.) □ Administration of contrast agent □ Imaging procedures or treatment procedures that involve radiation (x-rays, CT scans, CT-guided biopsies, DEXA scans, MUGA or PET scan) □ Biopsy conducted solely for research purposes □ Use of placebo □ Sham surgical procedure □ Collection of data from wearable tech such as Fitbit, Apple Watch, Garmin, motion actigraphs, etc.) 	

☐ Fitness tests or other exertion activities ☐ Use of mobile health apps or other apps

☐ Social media-based research activities☐ None of the above	
7.9 * PROCEDURES / METHODS: (REQUIRED)	
For clinical research, list all study procedures, tests and treatments required for this study, including when and how often they will be performed. If there are no clinical procedures, describe the research activities.	
If some of the activities would occur even if the person were not in the study, as in the case of treatment or tests performed for diagnostic purposes, clearly differentiate between those activities that will be done solely for research purposes and those that are happening as part of routine care.	
Examples may include:	
 additional scans outside standard clinical diagnosis or monitoring additional biopsies to collect tissue for research extra clinic visits extra lab tests not required for clinical care 	
If you have a procedure table, attach it to the submission with your other study documents.	
Patients will be randomized to intra-vaginal culture (IVC) of embryos using INVOcell or traditional in-vitro fertilization (IVF) of embryos. Both groups of patients will receive the same initial workup, consultation and evaluation, ovarian stimulation, cycle monitoring, oocyte retrieval, and embryo transfer. The only difference between the two groups will be the culturing/growth of the embryos, which will be randomized to IVC or IVF. All embryos will be transferred on day 3. The IVC protocol is attached for reference.	
7.10 STANDARD CLINICAL PRACTICE: To what extent, if any, do the planned research proc from the care that people would otherwise receive at this institution or the study site done locally:	

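### The trial is declared non-blinded throughout, yet the 6-week scan can be read without knowledge of the arm at almost no cost, and embryo grading, the outcome more open to reader bias, sometimes can be

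*Combined protocol and SAP*

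**What the plan says.** Sections 4.1 and 7.4 both label the design "Non-blinded prospective randomized controlled trial pilot study". Neither makes an exception for people who assess outcomes.

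The outcomes are defined in section 7.25. For the primary outcome the text is "Implantation rate, which is defined by number gestational sacs seen on early pregnancy 6-week ultrasound divided by number of embryos transferred". The clinical pregnancy rate counts fetal poles with a heartbeat on ultrasound. For the graded secondary outcome the text is "Embryo quality. This is measured by the Gardner grading system". On timing, the fertilization item states: "This comparison will take place on day-3, as that is when the IVC embryos will be assessed".

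Section 7.9 says of the arms: "The only difference between the two groups will be the culturing/growth of the embryos". It also says: "All embryos will be transferred on day 3". Section 7.13 adds that allocation is not made until the day of trigger.

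No supplied section names the embryo grader, the scan operator or the person who extracts the data, or says what they know of the allocation. Section 7.9 mentions an attached IVC protocol, which is not part of the supplied text.

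**The concern.** An open-label trial can still have masked outcome assessment, and here the two questions are treated as one. A woman knows whether she carried the device, and whoever opens it knows too. Neither fact requires the person counting sacs weeks later to know the arm.

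Embryo quality is where this matters most. A morphology grade is a judgment, and a grader who knows the arm can lean one way without intending to. The direction cannot be predicted, and nothing in the planned data would show afterwards whether it happened. The sac and heartbeat counts leave less room for judgment, but one of them is the primary outcome and the counts per arm are small.

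The pilot may lead to a larger trial (section 7.25). With only summary statistics planned, the raw rates are the result that would be carried forward. Unlike sampling error, reader bias does not shrink as the sample grows, and unmasked grades cannot be repaired later.

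**Working it through.** The plan has no power, margin or error rate tied to this point, so there is no figure to reproduce. Two checks apply.

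**1. Can the readers be masked on the plan's own terms?**

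- *Scan.* Section 7.9 makes culture the only difference between arms and puts every transfer on day 3. The scan in section 7.25 takes place at 6 weeks, so the device is no longer in use and nothing in the described care should show the arm on the image. The remaining routes are the chart and the woman herself.
- *Embryo grade.* Both arms are assessed on day 3, so a common reading time exists. Someone opens the device in one arm, and someone may have followed the incubator embryos in the other. A masked grader must have done neither. The documents do not describe laboratory staffing, so feasibility here is an inference.

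**2. How much does one reading weigh?**

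Inputs: 16 women per arm (sections 9.1 and 9.3) or 20 per arm (sections 7.25 and 10.6), with 1 to 3 embryos each (section 7.25). The two sample sizes conflict, which is a separate matter, so both are used. For this scaling I assume that all expected embryos are transferred and treat them as independent. Section 7.14 allows some to be frozen.

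Weight of one sac or embryo = 1 / (women per arm × embryos per woman).

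| Women per arm | Embryos each | Embryos per arm | One reading |
|---|---|---|---|
| 16 | 1 | 16 | 6.3 points |
| 16 | 3 | 48 | 2.1 points |
| 20 | 1 | 20 | 5.0 points |
| 20 | 3 | 60 | 1.7 points |

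For scale only, section 7.6 cites a non-randomized study of ICSI with the device against conventional ICSI:

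- Implantation 31.7% against 33.6%: gap 33.6 − 31.7 = 1.9 points. This equals 0.019 × 16 = 0.3 to 0.019 × 60 = 1.1 sacs per arm.
- Embryo quality 77% against 86.8%: gap 86.8 − 77 = 9.8 points. This equals 0.098 × 16 = 1.6 to 0.098 × 60 = 5.9 embryos per arm.

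An illustration with assumed behavior: take those quality rates as true and let a grader upgrade a fraction f of the lower-graded IVC embryos. The observed IVC rate is then 77 + 23f percent.

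- f = 0.10 gives 79.3%, gap 7.5 points.
- f = 0.20 gives 81.6%, gap 5.2 points.
- f = 0.426 gives 86.8%, gap 0.

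The documents give no basis for choosing any value of f.

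**Comparison with sampling error.** The 95% half-width of a difference is 1.96 × √[p₁(1 − p₁)/N + p₂(1 − p₂)/N], with N embryos per arm.

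- Implantation (0.336, 0.317): N = 16 gives 32.5 points; N = 60 gives 16.8 points.
- Embryo quality (0.868, 0.77): N = 16 gives 26.5 points; N = 60 gives 13.7 points.

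One reading is therefore small beside chance variation in every configuration.

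**The case against.** The strongest reply has four parts.

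*The label is accurate.* Section 7.4 asks for a brief description, and a trial whose women and device handlers know the arm is non-blinded. This stands: the label is not an error. The point is that it leaves out something cheap and useful.

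*A sac count is fairly objective, and the analysis is descriptive.* This largely stands. Bias in the primary outcome is probably small, and there is no test, margin or go/no-go rule for it to overturn. Sampling error is also much larger than the weight of one reading. What remains is that sampling error can be quantified and reader bias cannot.

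*The documents do not describe the readers.* This stands. A reader might infer that the treating team reads the scans, or that embryos are graded by staff who have just emptied a device. The supplied text says neither, and the attached IVC protocol might cover day-3 handling. A reader might also infer that the investigators would lean toward the device. The similarity hypothesis in section 4.1 concerns clinical pregnancy rate, not embryo grade, and section 4.16 declares no financial interest.

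*Masked grading could be burdensome.* This stands in part. Recoding dishes would complicate identity control, and section 7.5 itself treats avoiding embryo mix-ups as important. A second embryologist may not be on duty. Masked grading should therefore be conditional and leave the normal identity labels in place.

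One further limit applies. If day-3 assessment influences how many embryos are transferred, it affects the denominator of the primary outcome, and masking the scan operator does not address that. The documents do not say how that number is decided.

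**Conclusion.** The concern holds as a low-cost improvement. The supplied text declares the whole trial non-blinded and is silent on who reads outcomes and what they know. Masking the scan reader is feasible on the plan's own description. Masking the embryo grader may be feasible but depends on staffing that is not described. Embryo quality is the outcome more open to reader bias; the sac count is less so.

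The range of 1.7 to 6.3 points is the arithmetic weight of one sac or embryo. It might be taken as the size of an expected bias, but no misreading rate is documented, so it cannot be. It also lies well below the sampling half-widths of about 17 to 33 points for implantation and 14 to 27 points for embryo quality. No sample size, power or error rate changes.

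The verdict assumes that the missing IVC protocol does not already provide for masked reading. The figures assume 1 to 3 embryos transferred per woman and independence between embryos.

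**What to change.** - **Section 7.4:** change the design to *open-label, with masked outcome assessment where feasible*.
- **Section 7.25, scans:** state that the operator of the sac and heartbeat scan is not told the arm, that the woman is asked not to reveal it, and that counts are recorded on a form that does not show it.
- **Section 7.25, embryo grade:** where existing staffing allows, have the grade recorded by an on-duty embryologist who neither handled the device nor followed the IVF embryos. Keep the laboratory's normal identity labels. Otherwise record the grade as unmasked.
- **Reporting:** state for each reading whether masking was kept, and interpret unmasked embryo grades with caution.

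The cost is wording, one form and minor scheduling. No participants or visits are added and treatment does not change. Masking will be incomplete, since the woman or the chart may reveal the arm and some days may have only one embryologist.
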